## **Project Objectives**

The general objective of this project is to adapt the values alignment intervention to improve obesity-related eating habits in Spanish adolescents. It is therefore a highly innovative project with great potential for social impact in the field of health promotion. The specific objectives

are: (1) to adapt the values alignment intervention to the Spanish culture and context, (2) to evaluate the effects of the intervention in reducing unhealthy food intake and increasing healthy food intake in adolescents, (3) to evaluate differences between adolescents receiving the intervention and those in the control group regarding attitudinal variables related to healthy eating (alignment of healthy eating habits with adolescents' values and social attractiveness of healthy eating), (4) to evaluate potential moderators of the effect of the intervention, specifically socioeconomic status, given that more disadvantaged socioeconomic levels are associated with worse eating habits and greater obesity, gender, given that in the study by Bryan et al. (2019) the effect was more beneficial in boys, and body mass index (BMI), given that those adolescents with a higher BMI may present more consolidated habits of unhealthy food consumption, and (6) to evaluate whether the effect of the intervention on eating behavior is mediated by attitudinal variables.

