## **Methodology**

**Sample:** The study will be carried out with adolescents in the second and third years of high school in Bizkaia (Spain). The necessary estimated sample size is 500, under a small, anticipated effect size (0.2), a statistical power of 0.8, and a probability level of 0.05. In anticipation of a loss of participants during the follow-ups, the sample size will be increased to 600. Inclusion criteria include adequate reading comprehension and parental and self-informed consent.

**Design and Procedure:** A randomized controlled trial with two groups will be used. Randomization will be done by clusters, using the classroom as the unit. First, the schools will be selected according to their characteristics. Then, for each school and grade, half of the classrooms will be randomly assigned to the experimental condition (values alignment) and the other half to the control condition (traditional educational intervention). Participants will complete an online assessment protocol using Qualtrics, which will be composed of different questionnaires at three time points: (1) pretest (immediately before the intervention), (2) posttest (one week after the intervention), and (3) a three-month follow-up. The study has the approval of the Ethics Committee of the University of Deusto. The trial will be registered on ClinicalTrials.gov.

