**Statistical Analysis:** To evaluate the effect of the intervention on the repeated measures of the dependent variables, a multilevel analysis with MPLUS-8.8 will be used. This will include repeated measures at level one (e.g., healthy and unhealthy food intake), adolescent variables at level two (assigned intervention and potential moderators), and the classroom at level three. It will be determined whether the intervention explains the slope of change of the dependent variables (intervention  $\times$  time interaction). For moderation effects, triple interaction terms will be created using dummy variables or z variables, depending on the nature of the variables. To assess whether the effect of the intervention on healthy and unhealthy food intake is mediated by the attitudinal variables, a structural equation model with a bootstrapping procedure will be estimated ( $N = 10,000$  samples). For the handling of missing values, the full information maximum likelihood method will be used as a general approach, although, depending on the nature of the missing value patterns, other techniques (e.g., multiple imputations or use of auxiliary variables) may be used.

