#### BUDGET

Concept	Amount
Contract for a research assistant with a degree in psychology on a part-time basis (25 hours per week).	20,000
Travel and per diem expenses for researchers [name] and [name] for coordination and adaptation of the intervention materials for Spanish adolescents.	6,100
Incentive vouchers for participants. Vouchers will be raffled among the participants in each classroom to encourage participation. These will have a value of 20 euros and can be exchanged in shopping centers. Two vouchers will be raffled in each of the approximately 30 classrooms.	1,200
Trips to schools.	1,100
Expendable materials, such as markers and paints for intervention activities, which will be given to the adolescents.	1,600
Total	30,000
QUARTERLY WORK PLAN	1 2 3 4
1. Adaptation of the materials for Spanish adolescents	x
2. Acquisition of materials	x
3. Training the research staff on the procedures	x
4. Contacting schools and obtaining permissions	x
5. Application of pretest and intervention measures	x x x
6. One-week and three-month follow-ups	x x
7. Merging and cleaning of databases	x
8. Statistical analysis of data	x x
9. Writing the final report and scientific manuscripts	x
10. Dissemination and transference in conferences, participating schools, and society in general	x

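### Classrooms are randomised, but the plan enters the intervention as a pupil-level variable, makes no provision for change over time to vary by classroom, and gives the mediation bootstrap no classroom level or resampling unit

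*Combined protocol and SAP*

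**What the plan says.** Methodology, Design and Procedure: "Randomization will be done by clusters, using the classroom as the unit". Allocation is stratified: "for each school and grade, half of the classrooms will be randomly assigned to the experimental condition". The number of classrooms appears only in the Budget: "Two vouchers will be raffled in each of the approximately 30 classrooms".

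Methodology, Statistical Analysis, is the only analysis text. Repeated measures are at level one, with "adolescent variables at level two (assigned intervention and potential moderators), and the classroom at level three". The test is the intervention by time interaction: "It will be determined whether the intervention explains the slope of change of the dependent variables". The random effects at the classroom level are not listed, so the reader cannot tell whether there is only an intercept or also a time effect.

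The last numbered item under Project Objectives is "to evaluate whether the effect of the intervention on eating behavior is mediated by attitudinal variables". For this, "a structural equation model with a bootstrapping procedure will be estimated", with 10,000 samples. The three-level structure is described only for the repeated-measures analysis. The mediation sentence names no level, no cluster option and no unit to be resampled. Under Measurements, the two attitudinal mediators are taken at posttest and three-month follow-up only, so they have no pretest.

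**The concern.** Every pupil in a classroom has the same assignment, so the evidence on the intervention comes from about 30 units. An analysis of change must let those units differ in change.

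Naming the classroom as level three does not secure this. A classroom random intercept is the same at every wave. In balanced data it drops out of a pupil's change exactly, and with some missing waves nearly so. A model with that intercept alone treats pupils' changes as independent within a classroom. If classrooms in fact change by different amounts (through the teacher, the session or the peer group), the standard error of the intervention by time effect is too small.

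The mediation analysis has a parallel gap. If pupils are resampled one by one, the bootstrap distribution leaves out the classroom variation in the mediator, and the path from intervention to mediator looks more precise than it is. Because the mediators have no pretest, the ICC that matters here is that of the mediator's level, not of its change.

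At stake are the interval for the main intake effect and the rate at which indirect effects are declared.

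**Working it through.** **Inputs.** From the documents: about 30 classrooms (Budget); 600 pupils recruited and 500 required (Sample). Hence m = 600/30 = 20 pupils per classroom, or 500/30 = 16.7 if only 500 are analysed. Assumed, because the documents give none: ICC values of 0 to 0.10, equal classroom sizes, and a mediator-outcome path b of 0.05 to 0.4. The ICC is the between-classroom share of variance within school-grade strata, unless stated otherwise.

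**The plan's own figure.** The plan's 500 is for effect size 0.2, power 0.8 and level 0.05. The two-group formula gives 2 × (1.96 + 0.84)² / 0.2² = 393 per arm after rounding up, or 786 in all, so 500 is not reproduced without an unstated assumption. The step from 500 to 600 corresponds to 500 / (1 − 1/6). Nothing below depends on the 500 except the 16.7 pupils per classroom.

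**Slope test with a classroom intercept only.** Set the total variance of pupil change to 1. The true variance of the arm difference exceeds the modelled one by r = m × ICC + (1 − ICC). The true two-sided error is 2 × [1 − Φ(1.96/√r)]. For m = 20 and ICC 0.05, r = 1.00 + 0.95 = 1.95, √r = 1.396, 1.96/1.396 = 1.404, and the error is 16.0%.

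If half of the classroom variance is shared by the whole school-grade stratum, stratified allocation balances that half. Then r = m × ICC/2 + (1 − ICC); at ICC 0.05, r = 0.50 + 0.95 = 1.45 and the error is 10.4%.

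| ICC of change | m = 20 | m = 16.7 | m = 20, half shared by stratum |
|---|---|---|---|
| 0 | 5.0% | 5.0% | 5.0% |
| 0.01 | 7.2% | 6.8% | 6.0% |
| 0.02 | 9.5% | 8.7% | 7.1% |
| 0.05 | 16.0% | 14.2% | 10.4% |
| 0.10 | 25.0% | 22.1% | 15.5% |

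Simulation of 40,000 null trials per cell (30 classrooms of 20, no strata) gives 5.1 / 7.3 / 9.6 / 16.4 / 25.1% for the intercept-only model. Adding a classroom time effect, with restricted maximum likelihood (REML) and t on 28 degrees of freedom, gives 3.3 to 5.0%. The same model with maximum likelihood and a normal reference gives 4.5 to 6.9%, so the reference distribution matters with this few classrooms.

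**Mediation.** Simulated with no effect on the mediator, the same ICC for mediator and outcome residual, and 95% percentile intervals (67,500 null trials per cell, 1,000 resamples each). The false-positive rate when pupils are resampled is:

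| ICC | b = 0.2 to 0.4 | b = 0.1 | b = 0.05 |
|---|---|---|---|
| 0 | 5.0–5.3% | 2.8% | 0.9% |
| 0.01 | 7.4–7.6% | 4.3% | 1.3% |
| 0.02 | 9.6–9.7% | 5.6% | 1.7% |
| 0.05 | 16–17% | 10% | 3.0% |
| 0.10 | 25–26% | 16% | 5.5% |

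Resampling whole classrooms within arm gives 7.0 to 7.2% at b = 0.2 to 0.4, whatever the ICC. A stand-in for a multilevel model (intervention path from classroom means with t on 28 degrees of freedom, b path pooled within classrooms; not a full structural equation fit) gives 5.0 to 5.3%.

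**Cost in precision.** Relative to the intercept-only interval, a valid one is wider by about √r × 2.048/1.96. At ICC 0.05 this is 1.396 × 1.045 = 1.46, and simulation with REML gives 1.45. At ICC 0.01 the formula gives 1.14 and simulation 1.15. At ICC 0 the simulated factor is 1.10, because an estimated variance cannot fall below zero.

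**The case against.** The strongest reply is that the plan already has a classroom level and says that the intervention is to explain the slope. A classroom random time effect fits that wording, and the document is a short proposal in which random-effects detail may simply have been left out. This stands in part. A reader might infer that the plan ignores clustering, or that it commits to an invalid test. The documents do not support either reading: the classroom is level three, and nothing excludes the correct model. Nor does listing the intervention at level two shrink a standard error by itself; what matters is whether change may vary by classroom.

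What remains is more than missing detail. Followed as written, the plan tests a classroom assignment as a pupil characteristic acting on change. The mediation sentence, followed as written, is a single-level model.

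A second reply is that the harm may be small. That is fair. At an ICC of zero there is no inflation, so it would be wrong to say that the test is valid only with a classroom time effect. If strata share half of the variance, the error is 6 to 7% at ICC 0.01 to 0.02. For mediation, a weak b path hides the problem, the figures assume no effect on the mediator, and the plan's background reports attitudinal differences in earlier trials. Classroom resampling also gains almost nothing at ICC 0.01.

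**Conclusion.** The point holds as a failure to specify, and should be fixed before the data are seen. If change varies by classroom and the model does not allow it, the main test is too liberal: about 7% at an ICC of change of 0.01, 9.5% at 0.02, 16% at 0.05 and 25% at 0.10, against a nominal 5%. Mediation with pupil resampling is inflated by similar amounts at b = 0.2 to 0.4, for the ICC of the mediator's level.

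The omission is certain; the size is not. It rests on assumed ICCs, on about 30 classrooms of equal size, and on near-balanced data. A reader might take 25% as the expected error rate, but it is only the top of an assumed range, and the documents give no ICC from which to choose a value.

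**What to change.** (a) **Main model.** Enter the intervention as a classroom-level predictor of the slope, with a classroom random intercept and a classroom random time effect. Use classroom-based degrees of freedom: 30 − 2 = 28 for 30 classrooms in two arms. If the software offers no t reference, apply it to the estimate and its standard error. Keep full information maximum likelihood. A comparison of classroom mean changes is only a sensitivity check, because it drops pupils with missing waves.

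State whether school-grade strata enter as stratum-by-time terms. Leaving them out is safe but conservative if strata share variance. Including them leaves 30 − 5 − 1 = 24 degrees of freedom with 5 strata, or 30 − 15 − 1 = 14 with 15; the number of schools is not stated.

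(b) **Mediation.** Fit a multilevel structural equation model with the intervention at classroom level. Otherwise resample whole classrooms within arm, and note that this stays slightly liberal (about 7%). State which is used.

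**Cost.** Wording and model syntax; no extra data or participants. Slope intervals widen by about 1.10 times at an ICC of 0, 1.15 at 0.01 and 1.45 at 0.05. Real power is therefore below what an analysis ignoring classroom variation in change would suggest. If such an analysis had 80% power (expected z of 2.80), a classroom-based t test on 28 degrees of freedom would have about 77%, 70% and 49% at those three ICCs. Most of that loss at 0.05 reflects the clustering itself; recovering it would take more classrooms.

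### Classrooms are randomised within school and grade but the model contains neither, so precision is lost wherever schools or grades differ in the contrast being tested

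*Combined protocol and SAP*

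**What the plan says.** Under Methodology, the Design and Procedure paragraph states "Randomization will be done by clusters, using the classroom as the unit", and then that "for each school and grade, half of the classrooms will be randomly assigned to the experimental condition", with the other half going to control. This is stratified cluster randomisation, with school-by-grade cells as strata.

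The Statistical Analysis paragraph gives the model: repeated measures at level one, then "adolescent variables at level two (assigned intervention and potential moderators), and the classroom at level three". The test is "whether the intervention explains the slope of change of the dependent variables", that is, the intervention-by-time interaction. School and grade are neither levels nor covariates. They do not enter as moderators either: Project Objectives lists socioeconomic status, gender and BMI. The text does not say whether the time slope may vary between classrooms.

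The Measurements paragraph gives food intake three occasions including a pretest. The two attitudinal variables are measured only at posttest and three months. The Budget puts the number of classrooms at about 30.

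**The concern.** When every stratum contributes classrooms to both arms, differences between strata drop out of the true sampling error of the arm comparison. A model that ignores the strata still sees those differences as variation between classrooms and carries them into the standard error. The reported interval is then wider than the design warrants, the test runs below its nominal 5%, and power is lower than it could be. With about 30 classrooms and an anticipated effect of 0.2, there is little precision to spare.

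The extent depends on whether strata differ in the quantity actually tested. A difference in level between schools matters when arms are compared on level. When arms are compared on change from pretest, only a difference in change matters.

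**Working it through.** **The plan's own figure.** "The necessary estimated sample size is 500", with "a statistical power of 0.8" and "a probability level of 0.05" at effect size 0.2. Read as a standardised difference between two independent means, two-sided, this needs 2 × (1.96 + 0.84)² / 0.2² ≈ 393 per arm, or 786 in total (620 one-sided). So 500 does not reproduce. That is a separate matter; below, 500 and 600 serve only as numbers of pupils.

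**Inputs from the documents.** J = 30 classrooms (approximate); 500 pupils (16.7 per classroom) or 600 (20 per classroom); effect 0.2, read as SD units; alpha 0.05, taken as two-sided.

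**Inputs assumed.** The ICC, the share of it lying between strata, all variances of change, and 10 strata (for example 5 schools × 2 grades). Near-equal allocation within strata is also assumed; three classrooms per stratum cannot be halved exactly, so the figures are approximate.

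**Attitudinal outcomes, comparison of levels, 500 pupils.**
- Variance of a classroom mean without strata: ICC + (1 − ICC)/16.7.
- With strata: ICC × (1 − share) + (1 − ICC)/16.7.
- SE = √(4 × variance / 30).
- Power from the noncentral t, with 30 − 2 = 28 df without strata and 30 − 10 − 1 = 19 df with them.

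For ICC 0.05 and share one half, the variances are 0.05 + 0.057 = 0.107 and 0.025 + 0.057 = 0.082. The SEs are √(4 × 0.107/30) = 0.119 and √(4 × 0.082/30) = 0.105.

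| ICC | Share between strata | SE without → with | Power without → with |
|---|---|---|---|
| 0.05 | 50% | 0.119 → 0.105 | 37% → 44% |
| 0.10 | 50% | 0.143 → 0.118 | 27% → 36% |
| 0.02 | 25% | 0.102 → 0.099 | 47% → 48% |
| 0.05 | 0% | 0.119 → 0.119 | 37% → 36% |

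The actual size of the test without strata is about 2 × (1 − Φ(1.96 × SE without / SE with)): 2.5% in the first row and 1.7% in the second.

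**Food intake, intervention by time.** A generalised least squares calculation of the three-level model (32 classrooms of 19 pupils, balanced, three occasions, classroom random slope included) separates level from change:
- Stratum variance in level of 0, 0.05 or 0.20: SE of intervention by time is 0.0522 each time, with or without strata.
- Stratum variance in slope of 0.005, 0.01 or 0.02: model SE is 0.058, 0.063 or 0.072 without strata, against 0.0522 with stratum-by-time terms. The true SE stays at 0.0522.

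For power on the pretest-to-later change, take 600 pupils, pupil change variance 0.8 and classroom change variance 0.02. SE without strata = √(4 × (stratum variance + 0.02 + 0.8/20)/30). With strata the first term drops out, giving √(4 × 0.06/30) = 0.089.

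| Stratum variance of change | SE without | Power without (28 df) | Power with (19 df) |
|---|---|---|---|
| 0 | 0.089 | 58% | 56% |
| 0.01 | 0.097 | 52% | 56% |
| 0.02 | 0.103 | 46% | 56% |
| 0.05 | 0.121 | 36% | 56% |

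**If the model has no classroom random slope.** With the same pupil variance, and classroom and stratum change variances both 0.02, the model SE is √(4 × 0.84/600) = 0.075 against a true SE of 0.089. Type I error is then about 10%. Classroom variances of 0.01 and 0.04 (stratum 0.01 and 0.02) give about 8% and 15%.

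**The case against.** The strongest objection is that the tested effect for food intake is a difference in change. A reader might infer that all between-school and between-grade variance stays in the error for every intervention effect. The documents do not support this: food intake has a pretest, the contrast is intervention by time, and stable differences cancel from it. This stands. The level-comparison power figures therefore do not describe the food-intake test.

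A reader might also infer that the planned standard errors are certainly too large. That needs a classroom-level random slope, on which the plan is silent. Without one, the food-intake SE may be too small. This stands too.

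Third, the size rests on assumed inputs and could be negligible. At ICC 0.01 with a quarter between strata, power stays at about 52% with 10 strata. With 15 strata of two classrooms (14 df), which about 30 classrooms would allow, it falls slightly to about 50%. This limits the size that can be claimed, not the direction of the argument.

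Finally, where the random slope is present the omission is conservative and introduces no bias, and a one-paragraph analysis description may leave out covariates that are intended. Both are fair. Still, a conservative test gives up precision that the randomisation has already secured, and the intention should be written down before the data are seen.

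**Conclusion.** The point holds in a limited form. The analysis does not reflect the stratified randomisation, and this costs precision in two places: level comparisons of the attitudinal outcomes, and school or grade differences in food-intake change if a classroom random slope is fitted. Under the assumptions shown, modelling the strata changes attitudinal power by anything from a 1-point loss to a 9-point gain. For food-intake change, it changes power from about 58%, 52%, 46% or 36% to about 56%, as stratum variance of change goes from 0 through 0.01 and 0.02 to 0.05. The documents do not fix where in these ranges the trial lies.

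Nothing here shows that the arm comparison is biased, or that the conclusions would be invalid through omission of the strata alone. This is a cheap improvement, held with moderate confidence.

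**What to change.** State in the Statistical Analysis paragraph that:
- every intervention model includes the randomisation strata, as school plus grade or as school-by-grade cells;
- the intervention-by-time models also include stratum-by-time terms, because main effects alone leave that standard error unchanged;
- the time slope is random at classroom level;
- error degrees of freedom are classrooms minus strata minus 1 (30 − 10 − 1 = 19 under the assumption above).

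The cost is a few lines of text and some degrees of freedom. It needs no new data, since school and grade must be known in order to randomise. If strata explain nothing, about 1 to 1.5 points of power are lost with 10 strata, and up to about 3 with 15. Using school and grade main effects with their time interactions, rather than the full cross, limits this: with 5 schools and 2 grades, 30 − (1 + 4 + 1) − 1 = 23 df remain.

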## **Justification for the Project**

Obesity in adolescence is associated with physical and mental health problems and predicts obesity in adulthood. Adolescence may be an ideal time to target interventions, as this is when numerous health-related habits are consolidated (Bryan et al., 2019). Several universal preventive interventions have been carried out in educational centers for the promotion of healthy eating habits. However, the results of reviews and meta-analyses have concluded that most are not cost-effective for producing long-term changes in the dietary preferences of young people (Ashton et al., 2019; Kobes et al., 2018).

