**Interventions:** The experimental group will receive the values alignment intervention (Bryan et al., 2016). This includes: (1) reading materials, such as recent journalistic works that expose the deceptive and manipulative marketing practices of food companies and the harmful effects of these practices on society, with particular emphasis on harm to young children and the economically disadvantaged. Stories from other young people will also be included in order to contribute to the perception of widespread outrage and to suggest how that outrage can be channeled into taking a stand against the injustice perpetrated by food companies by eating less unhealthy or healthier food, (2) writing exercises, such as a story with a brief statement of what the participants would tell a younger child about the ads, and (3) an interactive activity, called "Make It Real" in which they are shown pictures of food ads and allowed to write and draw about them, making whatever changes (e.g., crossing out and substituting words) they feel necessary to make the ad "real" (i.e., no longer misleading). The control group will receive a traditional educational intervention on nutrition and physical exercise. This will be of the same duration and will also include reading and writing exercises.

**Measurements:** Healthy and unhealthy food intake will be measured at pretest, posttest, and three-month follow-up using the questionnaire developed by Stok et al. (2015). It consists of

four items that provide an index of unhealthy eating. In addition, according to the content addressed in the intervention sessions in the posttest and three-month follow-up, two attitudinal variables will be evaluated: (1) the alignment of healthy eating habits with the values of adolescents using seven items from Bryan et al. (2019), and (2) the social attractiveness of healthy eating using three items from Bryan et al. (2019), and answered on a five-point scale. Finally, some individual characteristics will be measured through an ad hoc questionnaire: gender, age, socioeconomic status (education and parental profession), height, and weight (to determine BMI).

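### The only named test of effect is an intervention-by-time slope: for the attitudinal variables it measures persistence, not the between-arm difference of objective 3, and for intake its meaning depends on an unstated time coding

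*Combined protocol and SAP*

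**What the plan says.** All references are to the combined protocol and SAP.

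- **Test of effect** (Methodology, Statistical Analysis): a three-level model of occasions within adolescents within classrooms, in which "It will be determined whether the intervention explains the slope of change of the dependent variables", glossed there as the intervention-by-time interaction. No coding of time, contrast at a given visit or main visit is stated here or elsewhere. Dummy and z variables are mentioned only for the triple interaction terms of the moderation analysis.
- **Visits** (Methodology, Design and Procedure): a pretest immediately before the intervention, then "posttest (one week after the intervention), and (3) a three-month follow-up".
- **Outcomes by visit** (Methodology, Measurements): intake is measured at all three visits. For attitudes, "in the posttest and three-month follow-up, two attitudinal variables will be evaluated", and no pretest measurement is listed.
- **Objective 3** (Project Objectives): "to evaluate differences between adolescents receiving the intervention and those in the control group regarding attitudinal variables related to healthy eating".
- **Missing data** (Statistical Analysis): "For the handling of missing values, the full information maximum likelihood method will be used as a general approach".

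**The concern.** Objective 3 asks about a difference in level between the arms. A slope between two post-intervention visits is a different quantity: it asks whether that difference changed after the first week. An intervention that shifts attitudes within a week and holds the shift for three months is a complete success on objective 3, yet it has an expected slope of zero.

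For intake there is a pretest, so a slope can carry the treatment effect. What it estimates depends on how time enters the model. The first interval is short and the second long, so linear weeks, 0/1/2 and categorical time answer different questions from the same data. If the choice stays open until the data are in, the conclusion can turn on it.

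**Working it through.** The plan gives no figure for this test, so there is none to reproduce. The total of 500 and the effect size of 0.2 come from Methodology, Sample; how 500 was derived is a separate question.

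**Attitudes (algebra only)**

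Let D1 be the arm difference at posttest and D2 the difference at three months. With two occasions, the interaction is (D2 − D1) divided by the coded distance between them. Coding changes the divisor and nothing else.

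- Fully sustained effect, D2 = D1: slope 0.
- Fading effect, D2 < D1: slope negative.
- Effect that grows after posttest, D2 > D1: slope positive.

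Illustration, assuming D1 = 0.2 SD, between-visit correlation 0.5, 500 complete cases, no clustering, two-sided 0.05:

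- SE of the slope contrast = √(2 × 0.5 × 4/500) = 0.0894.
- Sustained: expected value 0, so significance occurs only at the 5% error rate.
- Half remaining: expected value −0.10, significantly negative in 20% of trials. A quarter remaining: −0.15 and 39%.
- Arm difference at posttest: SE = √(4/500) = 0.0894, z = 0.2/0.0894 = 2.24, power 61%.

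The last figure falls with clustering. The Budget states "Two vouchers will be raffled in each of the approximately 30 classrooms", which gives 500/30 = 16.7 pupils per classroom. With design effect 1 + 15.7 × ICC, power is 50%, 39% and 29% at assumed ICCs of 0.02, 0.05 and 0.10.

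**Intake (three visits)**

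With complete data and a random intercept, the slope over the full time range weights the arm differences by w = (t − mean t) × range / Σ(t − mean t)². Its SE is √[(1 − ρ) × Σw² × 4/N]. The length of the intervention and the starting point of the three months are not stated. So the week codings below are assumptions: 0/1/13 for an intervention of negligible length, and 0/3/15 and 0/4/16 if two or three further weeks separate pretest from posttest. Take d = 0.2 at both later visits, ρ = 0.5 and N = 500.

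| Coding | Weights | Sustained effect estimated as | SE | Power | Sign reverses if more than this share has faded |
|---|---|---|---|---|---|
| 0/1/13 | −0.580, −0.455, +1.035 | 0.58d | 0.0804 | 30% | 56% |
| 0/3/15 | −0.714, −0.357, +1.071 | 0.71d | 0.0845 | 39% | 67% |
| 0/4/16 | −0.769, −0.308, +1.077 | 0.77d | 0.0859 | 43% | 71% |
| 0/1/2 | −1, 0, +1 | 1.00d | 0.0894 | 61% | does not reverse |

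For 0/1/13, the mean is 4.667 and the sum of squares 104.67. The posttest weight is (1 − 4.667) × 13/104.67 = −0.455. The estimate is zero when 0.455/1.035 = 44% of the effect remains. Taking three months as 12 or 14 weeks gives 0.59d or 0.57d. At correlations of 0.3 and 0.7, power is 23% and 46% for 0/1/13, against 47% and 82% for 0/1/2.

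If the effect has gone entirely by three months, a significant result in the opposite direction occurs in 20% of trials for 0/1/13 and 11% for 0/4/16.

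If instead the effect grows linearly to 0.2 at week 13, the posttest difference is 0.2/13 = 0.0154. The weeks estimate is then 1.035 × 0.2 − 0.455 × 0.0154 = 0.200, with power 70% against 61% for 0/1/2.

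Dropout changes little. The plan allows for it: "In anticipation of a loss of participants during the follow-ups, the sample size will be increased to 600". With 600 enrolled, 100/600 = 16.7% missing only the last visit, and likelihood estimation, power is 32% for 0/1/13 and 67% for 0/1/2, where the posttest weight becomes +0.085.

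**The case against.** **Intake.** The plan never says that time will be coded in weeks. Three ordered occasions are often coded 0/1/2, which gives essentially the pretest-to-three-month change. That is a sensible target for a project whose rationale is that, of existing school programmes, "most are not cost-effective for producing long-term changes in the dietary preferences of young people". An interaction with time could also mean categorical time, which avoids the issue. This stands. A reader might infer that the intake analysis will halve the power or reverse the sign of the effect. The documents do not support that: both follow only from a coding they do not state, the size depends on an unstated intervention length, and weeks coding is the better choice under linear growth. What remains is that the coding must be fixed, and that under 0/1/2 the one-week result has almost no influence and no test of its own.

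**Attitudes.** Three points deserve weight.

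- The analysis paragraph illustrates the repeated measures with intake only and names attitudes explicitly only as mediators, so it is an inference, though the likelier reading, that the slope test covers them. If it does not, objective 3 has no named test at all.
- A model with an arm-by-time term normally carries an arm coefficient too. With time zero at posttest, that coefficient is the posttest difference. A reader might infer that the planned model cannot detect a sustained attitude effect; that goes too far. The coefficient is not named as the test, however, and the visit it describes depends on the unstated time origin. The mediation model is planned for a different question.
- A negative attitude slope is not an error. It correctly describes fading, and the 20% and 39% above are power to detect it. They mislead only if the slope is read as the treatment effect.

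**Conclusion.** The point holds, chiefly for the attitudinal variables. The one test the plan names measures whether an effect persisted between one week and three months, while objective 3 asks whether the arms differ. This is algebra and needs no assumed correlation, ICC or effect size. It rests on two readings of the text: that attitudes have no pretest measurement, and that they are among the dependent variables whose slope is tested.

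For intake the finding is an open specification, not a demonstrated fault. Under linear weeks the posttest takes negative weight in every timing tried. A sustained effect is then estimated at 0.58d to 0.77d with power of 30% to 43%, against 61% for 0/1/2; a linearly growing effect reverses the ranking (70% against 61%). These powers assume d = 0.2, correlation 0.5, 500 complete cases and no clustering, and are illustrations. The matter should be settled before analysis.

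**What to change.** **Attitudes.** For each of the two variables, test the intervention-control difference at posttest and at three months in the multilevel model with classroom as a level. Name one visit as main, and report the slope only as a description of persistence.

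**Intake.** Treat time as a three-category factor and adjust for pretest, by constraining pretest means to be equal between arms or by another valid baseline adjustment. Report the arm difference at posttest and at three months. Name in advance one visit and one intake outcome (healthy or unhealthy) as the main test, and build the moderator terms on the same contrasts. If a linear slope is kept, state the time coding and add the posttest contrast as secondary.

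**Cost.** SAP wording and model syntax; no new data or visits. There are more contrasts than one slope: two intake outcomes at two visits and two attitudes at two visits, four comparisons each. A main test or a multiplicity rule is therefore needed. Some power is lost against a weeks slope if the intake effect truly grows linearly. The gain over 0/1/2 comes from baseline adjustment and is modest: 70%, 67% and 65% against 61% at assumed ICCs of 0.02, 0.05 and 0.10, with classroom effects constant over time. An assumed classroom-by-visit variance of 0.01 would lower the 61% to about 50%. Constraining pretest means also assumes that knowledge of the allocation does not affect consent or pretest answers.
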